9.2.1. Baseline Measures

Baseline demographic, hospitalization and clinical characteristics will be assessed for the apixaban and warfarin cohorts, specifically among patients with their first outpatient index prescription (i.e. treatment index date) and with pharmacy stability. Demographic features will be measured on the patient’s treatment index date. Clinical characteristics will be assessed during the 6-months prior to the treatment-index date. Index hospitalization characteristics will also be assessed and reported for the apixaban and warfarin cohorts.

Baseline demographic characteristics (using LRx data)

- Age (years; mean, standard deviation [SD], median, interquartile range (IQR), min, max)
- Age group (18-34, 35-44, 45-54, 55-64, ≥65 years; n, %)
- Gender (male, female; n, %)
- Payer type (Third party, Medicaid, Medicare, Medicare part D, cash, other; n, %)
- Index date year (2018, 2019, 2020, 2021, 2022; n, %)

090177e19cc79c7fApproved\Approved On: 03-Mar-2023 00:48 (GMT)

- Follow-up duration (mean, SD, median, IQR, min, max)

Hospitalization characteristics (using CDM data)

- Hospital geographic region (Northeast, Midwest, South, West)
- Number of hospital beds (1-99 beds, 100-199 beds, 200-299 beds, 300-499 beds, 500+ beds)
- Hospital location (Rural, Urban)
- Teaching status (Teaching, Non-teaching)
- Admitting source (ER, referral and transfer, routine admission, other, unspecified)
- Discharge disposition (Alive – Home, Left Against Medical Advice or Discontinued Care [LAMA], Transferred – Long Term Care, Transferred – Other Institution, Transferred – Short-Term Hospital, Unknown/Other)
- Index VTE type (DVT only, PE only, DVT and PE; n, %).
- VTE etiology: (Provoked: VTE preceded by hormone therapy, fracture/trauma involving lower extremities, pelvic/orthopedic surgery, or hospitalization for any reason for ≥ 3 days during 3 months prior to index VTE event. Unprovoked: VTE events not classified as provoked)

Baseline clinical characteristics

- Prescribing provider specialty associated with the treatment index prescription in LRx (primary care [general practice/family practice/internal medicine/physician assistant/nurse practitioner], cardiologist, other, unknown; n, %) (Frequency table will be provided with details on provider specialty counts within ‘other’ category)
- Charlson Comorbidity Index (CCI, Dartmouth-Manitoba adaptation; mean, SD, median, IQR, min, max)
- CCI (categorical [0-1, 2, 3, 4+]); n, %)
- Comorbidities of interest (ICD-10 diagnosis codes in Dx or CDM; n, %)
 - Acquired immune deficiency syndrome (AIDS)
 - Alcohol/drug abuse
 - Anemia
 - Cerebrovascular disease
 - Coronary heart disease/ischemic heart disease
 - Congestive heart failure
 - Chronic obstructive pulmonary disease (COPD)
 - Coronavirus disease 2019 (COVID-19)

090177e19cc79c7f\Approved\Approved On: 03-Mar-2023 00:48 (GMT)

- Dementia/Alzheimer's disease
- Dyspepsia or stomach discomfort
- Diabetes mellitus
- Hemiplegia/Paraplegia
- Hematologic disorders associated with bleeding (thrombocytopenia)
- Hyperlipidemia
- Hypertension
- Inflammatory bowel disease
- Liver/Gall bladder/Pancreatic disease
- Obesity
- Peptic ulcer
- Peripheral vascular disease
- Pneumonia
- Renal disease
- Rheumatologic disease
- Sleep apnea
- Spinal cord injury
- Thrombocytopenia
- Thrombophilia
- Varicose veins
- Procedures of interest (ICD-10 diagnosis or procedure codes, CPT Codes, HCPCS codes in Dx or CDM; n, %)
 - Orthopedic surgery
 - Central Venous Catheter
- Baseline bleeds (ICD-10 diagnosis or procedure codes, CPT Codes, HCPCS codes in Dx or CDM; n, %)
 - Gastrointestinal
 - Intracranial
 - Others
- History of falls (ICD-10 diagnosis codes in Dx or CDM; n, %)
- Fracture/trauma involving lower extremities (ICD-10 diagnosis codes in Dx or CDM; n, %)

- Medications of interest (NDC or HCPCS codes in LRx or Dx; n, %)
 - Angiotensin-converting enzyme (ACE) inhibitors/Angiotensin receptor blockers (ARB)
 - Antiarrhythmic agents
 - Antiplatelet agents
 - Aromatase inhibitors
 - Beta blockers
 - Erythropoiesis stimulating agents (ESA)
 - Gastroprotective agents
 - Nonsteroidal anti-inflammatory drugs (NSAID)
 - Selective estrogen receptor modulators (SERM)
 - Statins

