9.1.2. Exclusion criteria

Patients meeting any of the following criteria will be excluded from the study:

1. Patients with hospitalization with a primary diagnosis of VTE in the 6-month pre hospitalization period
2. Patients with any OAC administration other than apixaban for apixaban cohort (except warfarin use before apixaban) or warfarin for warfarin cohort during hospitalization

Note: Apixaban cohort patients will be allowed to have warfarin prior to apixaban administration. At this step, we will also report the number of patients that have both apixaban and warfarin use during the hospitalization.

3. Patients with unfractionated heparin or low molecular weight heparin (LMWH) administration after apixaban (for apixaban cohort) or warfarin (for warfarin cohort) administration during hospitalization.

Note: that unfractionated heparin or LMWH prior to apixaban or warfarin will be allowed.

4. With ≥ 1 claim/record with a diagnosis code for atrial fibrillation/flutter in Dx or CDM during the hospitalization and in the 6-month pre hospitalization period
5. With ≥ 1 claim with a procedure code for mechanical heart valve in Dx or CDM during the hospitalization and in the 6-month pre hospitalization period
6. With ≥ 1 claim with a procedure code for inferior vena cava filter in Dx or CDM during the study period
7. With ≥ 1 claim with a diagnosis code or procedure code of pregnancy in Dx or CDM during the study period
8. With use of OAC or PAC (in LRx or Dx) (unless prophylactic) during the 6-month pre-hospitalization period

Note: The OAC or PAC prescription claim will be considered prophylactic if duration of the prescription is ≤ 42 days AND the start date of OAC or PAC occurs within 2 days before or 7 days after knee/hip replacement surgery

OR

Start date of OAC or PAC occurred within 7 days after the admission of a hospitalization associated with 'medically ill' (primary discharge diagnosis; codes provided separately) AND with a ≥ 3 -day length of stay of the hospitalization.

9. With data quality issues (invalid/missing enrollment dates, gender and payer type)

A preliminary attrition table will be provided to the Alliance for review, at which time modifications to the inclusion and exclusion criteria may be considered.

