9.6. Data analysis

Descriptive statistics will be produced for all relevant study measures previously described, for the overall cohort and for each treatment (apixaban and warfarin). Categorical measures will be presented using frequency (number of patients [n]) and percentage (%) of total study patients observed in each category. Continuous and count variables will be presented as the mean, SD, median, minimum, maximum and IQR. As relevant, continuous variables will also be categorized into intervals. Univariate statistics will be calculated for each measure of interest. No comparisons will be made between the two cohorts..

Four multivariable regression models will be developed for this study. Cox proportional hazards models will be conducted to evaluate both the risk (expressed as hazard ratios with corresponding 95% confidence intervals) of discontinuing or switching from the index treatment as well as the risk of experiencing a clinical event (i.e., recurrent VTE, major bleeding, or CRNM bleeding).. The main effect variable will be the treatment cohort (apixaban vs. warfarin, with warfarin as the reference group). Covariates to be considered for inclusion into the models will include demographic and clinical characteristics of interest. A backward elimination of independent variables least associated with the dependent variable may be used. Clinically relevant covariates that are not retained during backward elimination may also be forced into the model. Collinearity among the variables of interest will be evaluated during model development.

Kaplan-Meier analyses will also be utilized to report the time to an event of interest (e.g., switch, discontinuation). Kaplan-Meier is a method for estimating the probability of the proportion of individuals remaining in the sample at a particular time from an initiation point. It takes into account patients lost or censored before the study endpoint. All analyses will be based on observed, not projected, data. Analyses will be conducted using SAS[®] Release 9.4 (SAS Institute Inc., Cary, NC), and the results will be reported in Excel tables.

Any major modifications of primary endpoint definitions (treatment patterns) or their analyses would be reflected in a protocol amendment.

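### Cancer is not a provoking factor, a listed comorbidity or an exclusion, so cancer-associated VTE without a listed trigger is tabulated as unprovoked and the Cox models have no specified cancer covariate

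*Combined protocol and SAP*

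**What the plan says.** Section 9.2.1 (Hospitalization characteristics) sets the etiology rule: "Provoked: VTE preceded by hormone therapy, fracture/trauma involving lower extremities, pelvic/orthopedic surgery, or hospitalization for any reason for ≥ 3 days during 3 months" before the index event. The other class is defined only by default: "Unprovoked: VTE events not classified as provoked".

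The same section lists comorbidities to be found from diagnosis codes in Dx or CDM. The list has 28 entries, including dyspepsia, sleep apnea and varicose veins, and none is a malignancy. Overall comorbidity is summarized as "Charlson Comorbidity Index (CCI, Dartmouth-Manitoba adaptation; mean, SD, median, IQR, min, max" and in the bands 0-1, 2, 3 and 4+. The medication list includes "Aromatase inhibitors", selective estrogen receptor modulators and erythropoiesis stimulating agents. Central venous catheter is listed as a procedure.

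Section 9.1.2 has nine exclusion criteria, and none concerns cancer.

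Section 9.6 plans four multivariable models, with Cox models for discontinuing or switching and for recurrent VTE, major bleeding and CRNM bleeding. Treatment cohort is the main effect and warfarin the reference. On adjustment it says: "Covariates to be considered for inclusion into the models will include demographic and clinical characteristics of interest". Backward elimination may be used, and clinically relevant variables that it drops may be forced back in.

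**The concern.** Patients with cancer stay in the cohort, but the plan defines no variable that identifies them. Two outputs are affected.

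- **The etiology table.** The unprovoked row will mix events with no known cause and cancer-associated events that lack a listed trigger. A reader of the report could not tell the two apart.
- **The Cox models.** It is plausible, though the documents do not discuss it, that cancer bears on recurrence, bleeding, length of treatment and the choice between apixaban and warfarin. If so, it is a potential confounder of the apixaban-versus-warfarin hazard ratio. In addition, 9.2.2 counts a parenteral anticoagulant fill around run-out as a switch, so a cancer-related change of agent would be scored as a switch with no cancer term in the model.

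The background (Section 7) also says the study will investigate factors associated with poor outcomes. A condition with no variable cannot be reported as such a factor.

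**Working it through.** The plan states no figure on this point, so there is nothing to reproduce. The check has a textual part and an illustration on assumed inputs.

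**1. Where could cancer enter?**

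| Place | Finding |
|---|---|
| 9.1.2, exclusions | Nine criteria, none for cancer; these patients remain |
| 9.2.1, etiology | Four triggers, none is cancer; the rest are unprovoked |
| 9.2.1, comorbidities | 28 entries, no malignancy |
| 9.2.1, Charlson index | Total and bands only; components not listed |
| 9.2.1, medications | Aromatase inhibitors, SERMs and erythropoiesis stimulating agents: partial markers, not a cancer variable |
| 9.6, covariates | Pool described but not enumerated; no cancer term |
| 9.8, limitations | Cancer not mentioned |

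If the Charlson version used counts malignancy, cancer contributes points to a sum, and the sum does not show which condition supplied them. If it does not, only the drug markers remain.

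Section 9.2.1 separates demographic, hospitalization and clinical characteristics. Etiology and index VTE type are hospitalization characteristics, whereas the pool in 9.6 is demographic and clinical. Read literally, neither is a named candidate.

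**2. Which cancer cases are labelled unprovoked?** Only those without a listed trigger. A stay of at least 3 days for any reason in the preceding 3 months, or any other listed trigger, makes a cancer case provoked. Hormone therapy is not defined, so it is unclear whether aromatase inhibitors or SERMs count.

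Let c be the share of patients with cancer and t the share of those with at least one listed trigger. Both are assumed. The share of all patients who have cancer and are labelled unprovoked is c × (1 − t).

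- Low end: c = 5%, t = 60%: 0.05 × 0.40 = 2%.
- High end: c = 20%, t = 20%: 0.20 × 0.80 = 16%.

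The rest of the cancer cases, a share t of them (20-60%), fall under provoked.

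**3. What could omission do to the treatment contrast?** Let pA and pW be cancer prevalence in the apixaban and warfarin cohorts, and RR the factor by which cancer raises the event rate, taken as equal in both. With no adjustment, the rate ratio is multiplied by (1 + pA(RR − 1)) / (1 + pW(RR − 1)).

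| pA | pW | RR = 2 | RR = 3 |
|---|---|---|---|
| 10% | 10% | 1.10/1.10 = 1.00 | 1.20/1.20 = 1.00 |
| 15% | 10% | 1.15/1.10 = 1.05 | 1.30/1.20 = 1.08 |
| 10% | 15% | 1.10/1.15 = 0.96 | 1.20/1.30 = 0.92 |
| 20% | 10% | 1.20/1.10 = 1.09 | 1.40/1.20 = 1.17 |
| 10% | 20% | 1.10/1.20 = 0.92 | 1.20/1.40 = 0.86 |

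Every input is an assumption. Partial adjustment through the Charlson total should generally bring these factors closer to 1.

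**The case against.** The strongest reply is that the plan leaves room to deal with cancer. The covariate list is open, clinically relevant terms may be forced in, diagnosis codes are available in Dx and CDM, and the Charlson total may carry some of the effect. Part of this stands. A reader might infer that cancer cannot be separated or adjusted for, and the documents do not support that: the data exist, and the plan merely specifies no such variable. But the forcing rule acts on variables that elimination has dropped, and no cancer variable is defined to be among them.

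A second reply is that the four triggers catch many cancer patients. This also stands. A reader might infer that all cancer-associated VTE is reported as unprovoked; in fact the cases are split across both classes.

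Third, a reader might infer that the recurrence rate of the unprovoked group will be overstated. No such result is planned. Section 9.2 evaluates outcomes by treatment cohort, and 9.6 describes results overall and by treatment. Etiology is a baseline descriptor.

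Fourth, etiology is tabulated in a selected group: treated in hospital with apixaban or warfarin, no heparin after the oral agent during the stay, no vena cava filter, no earlier non-prophylactic anticoagulant, and a matching outpatient fill. Cancer prevalence there may differ from that in all VTE admissions. That is correct, and it is why no prevalence is asserted here.

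Finally, the code lists are not part of the text reviewed. They could contain malignancy codes, but the protocol names no variable that would use them. Section 9.6 also says that no comparisons will be made between cohorts, yet it specifies treatment cohort as the main effect, so confounding of that hazard ratio remains relevant.

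**Conclusion.** The point holds in a limited form. By the plan's own rule, cancer-associated VTE without one of the four triggers is tabulated as unprovoked, and no stand-alone cancer covariate is specified for the models that estimate apixaban versus warfarin. The mixed etiology row follows directly from the text wherever such patients are present. Bias in the hazard ratios is possible but not shown: its size and direction depend on prevalences and effects that the documents do not give. The range 0.86 to 1.17 rests on an assumed prevalence of 10% against 15-20%, a 2-3 fold effect of cancer and no other adjustment. Equal prevalence gives no shift. The change should be made because the rule and the variable list as written are weaker than the planned data sources allow, and the correction is cheap.

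**What to change.** 1. Add active cancer to the baseline comorbidities in 9.2.1, with a code list, identified in Dx or CDM during the 6-month baseline.
2. Report cancer-associated VTE as its own etiology level beside provoked and unprovoked, and state which level takes precedence when a cancer patient also has a listed trigger.
3. In 9.6, name active cancer, etiology and index VTE type as prespecified candidate covariates in the models, with active cancer forced in. If etiology is entered with its cancer level, check that it does not duplicate the active-cancer term.
4. Optionally, repeat the persistence and clinical-outcome analyses without cancer patients as a sensitivity analysis.

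Central venous catheter need not become a trigger. It is already collected and can be considered as a covariate.

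The cost is one code list, one more table row and one extra model term, with no new data source. The optional sensitivity analysis would add further output tables.

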9.2.2. Outcome measures

The following outcome measures are assessed post-discharge, and will be measured during the variable post-index period starting on the treatment index date for the apixaban and warfarin cohorts.

Treatment patterns

- Persistent days (mean, SD, median, IQR, min, max) will be reported for patients until they discontinue, switch or end of follow-up based on definitions below
- Patients discontinuing outpatient treatment of apixaban or warfarin, respectively (NDC codes from LRx; n, %)

Note: Discontinuation will be defined as the occurrence of a ≥ 30 day gap from the run-out of days' supply of the treatment (post-discharge) index prescription (i.e. apixaban or warfarin) to the date of the next claim for the respective therapy or with no other claims for the respective therapy. The date of the discontinuation will be defined as the last day of the days' supply of the last filled prescription.

- Time (in days) from treatment index date to discontinuation date (mean, SD, median, IQR, min, max)

Note: Kaplan-Meier (KM) curves will be generated to measure median time (and 95 % CI) to discontinuation.

- Patients switching to an OAC other than apixaban or warfarin, respectively (switched) (NDC codes from LRx; n, %)

Note: Patients will be considered to have switched if they filled a prescription for OAC other than apixaban or warfarin, respectively (identified through NDC codes in LRx) or for PAC within 30 days before or after the run out date of index treatment. The date of the switch will be defined as date of the prescription of such a therapy (OAC or PAC).

- Time (in days) from treatment index date to switch date, defined as the date of the first claim for the new OAC or PAC (mean, SD, median, IQR, min, max)

Note: KM curves will be generated to measure median time (and 95 % CI) to switching

Clinical Outcomes

The following clinical outcomes will be assessed during the time patients are persistent with their respective index apixaban or warfarin treatment (treatment index):

- Patients with ≥ 1 hospitalization for recurrent VTE (ICD-10 codes in CDM; n, %)
- Incidence rate (IR) of recurrent VTE (per 100 patient years)
 - The date of the first observed event will be flagged. The numerator for IR will be the number of patients with the event of interest and denominator will be the ‘at risk’ period i.e. the time to first event. The 95% confidence intervals (CI) will also be reported.

Note: Recurrent VTE will be defined as inpatient hospitalization with a primary diagnosis of VTE occurring 7 or more days after the first hospitalization discharge date.

- Time (days) from first hospitalization discharge date to first recurrent VTE hospitalization (mean, SD, median, IQR, min, max)
- Time (days) from treatment index date to first recurrent VTE hospitalization (mean, SD, median, IQR, min, max)
- Patients with ≥ 1 hospitalization for major bleeding (ICD-10 codes in CDM; n, %)
- IR of major bleeding (per 100 patient years)

Note: Major bleeding will be defined as inpatient hospitalization with primary diagnosis of gastro-intestinal bleeding, intracranial hemorrhage (ICH) or other major bleeding

- Time (days) from first hospitalization discharge date to first major bleeding episode (mean, SD, median, IQR, min, max)
- Time (days) from treatment index date to first major bleeding episode (mean, SD, median, IQR, min, max)
- Patients with ≥ 1 CRNM bleeding event (n, %)
- IR of CRNM bleeding (per 100 patient years)

Note: CRNM bleeding will be defined as inpatient hospitalization with a secondary diagnosis code for bleeding (without a major bleeding code in the primary position) or an outpatient encounter with a diagnosis code in any position for CRNM GI bleeding or other non-critical types of bleeding. Specifically, it is defined as:

(1) An inpatient admission with a secondary diagnosis for “noncritical site” bleeding such as GI bleeding or other selected noncritical types/sites of bleeding (excluded if major bleeding occurred during the same hospitalization), OR

(2) An outpatient encounter with a diagnosis code for GI bleeding and other selected noncritical types/sites of bleeding.

Any CRNM bleeding events (as described above) that follow a major bleeding event (described above) will not be included in the analysis of CRNM bleeding

- Time (days) from first hospitalization discharge date to first CRNM bleeding episode (mean, SD, median, IQR, min, max)
- Time (days) from treatment index date to first CRNM bleeding episode (mean, SD, median, IQR, min, max)

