7. RATIONALE AND BACKGROUND

Venous thromboembolism (VTE), comprising deep vein thrombosis (DVT) and pulmonary embolism (PE), is a major health concern associated with significant mortality and morbidity. It is the third most common cause of vascular disease-related death and poses a substantial economic burden to the healthcare system. In the United States (US), approximately 1 million people develop symptomatic VTE each year.^{1,2} There are >330,000 hospital admissions for VTE every year in the United States (US).³ Historical data suggests that the rate of hospitalizations for VTE increased from 7.0 to 8.4 per 1,000 discharges in the US.⁴

Management of VTE during an acute hospital encounter involves rapid anticoagulation. Current guidelines recommend continuing anticoagulation therapy post-discharge with vitamin K antagonists such as warfarin, or one of the newer direct oral anticoagulants (DOAC) which do not require PAC bridging therapy.⁵ Over the past decade, the use of DOACs, particularly apixaban to treat VTE has increased dramatically.⁶

There are some gaps in RWE regarding OAC use among patients hospitalized with VTE. First, there is need for RWE regarding the proportion of patients treated with particular OAC during the VTE hospitalization. Second, there needs to be a better understanding of the OAC-related treatment patterns post-discharge following VTE hospitalizations. There is evidence that a large proportion of patients treated in inpatient and observational hospital settings do not fill an anticoagulant prescription post-discharge⁷. Research shows that the choice of treatment regimen and/or setting could influence the likelihood of post-discharge continuation of OAC medication.⁷ This study will investigate the initial treatment patterns during VTE hospitalization and further investigate the treatment patterns and factors associated with poor outcomes among these patients.

The study team, comprised of members from Pfizer and Bristol Myers Squibb (hereon referred to as the 'Alliance'), is collaborating with IQVIA in conducting a study to assess treatment patterns and health outcomes post hospital discharge for VTE.

090177e19cc79c7f\Approved\Approved On: 03-Mar-2023 00:48 (GMT)

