8. RESEARCH QUESTION AND OBJECTIVES

The purpose of this study is to evaluate the post-discharge treatment patterns including persistence and outcomes such as recurrent VTE and bleeding among hospitalized adults with VTE treated with apixaban or warfarin.

The study objectives are to:

1. Describe the proportion of patients with VTE treated with apixaban or warfarin in the hospital
2. Understand the post-discharge treatment patterns (including persistence, switch, and discontinuation) among patients who started on apixaban or warfarin in the hospital

The secondary objective is to:

3. Assess recurrent VTE, major bleeding, and clinically relevant non-major (CRNM) bleeding among patients who continue on apixaban or warfarin in the outpatient setting while persistent on index therapy

[figure not shown]

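### The persistent-days summary pools censored with completed durations, and no censoring-aware duration is specified for the composite (first of discontinuation or switch) that defines persistence

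*Combined protocol and SAP*

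**What the plan says.** Objective 2 in section 8 is to "Understand the post-discharge treatment patterns (including persistence, switch, and discontinuation) among patients who started on apixaban or warfarin in the hospital", and it is not labelled secondary. Section 9.6 places treatment patterns in the primary tier: "Any major modifications of primary endpoint definitions (treatment patterns) or their analyses would be reflected in a protocol amendment".

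Section 9.2.2 then gives three duration measures:

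- **Persistence:** "Persistent days (mean, SD, median, IQR, min, max) will be reported for patients until they discontinue, switch or end of follow-up". No Kaplan-Meier note is attached.
- **Discontinuation:** raw time to the event, plus the note "Kaplan-Meier (KM) curves will be generated to measure median time (and 95 % CI) to discontinuation".
- **Switching:** raw time to the event, plus the note "KM curves will be generated to measure median time (and 95 % CI) to switching".

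Section 9.6 adds that "Kaplan-Meier analyses will also be utilized to report the time to an event of interest (e.g., switch, discontinuation") and says of the method: "It takes into account patients lost or censored before the study endpoint". It also plans Cox models for discontinuing or switching, with treatment cohort as the main effect, while ruling out other comparisons between cohorts.

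Under section 9.2, follow-up closes at whichever comes first among the final prescription, the final medical claim, loss of pharmacy stability and the close of the study period. Index year and follow-up duration are reported as baseline measures (section 9.2.1).

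**The concern.** For a patient still on treatment at the end of follow-up, the recorded persistent days are a lower bound, not a duration. Taking the mean and median of such values as if complete estimates the distribution of min(T, C), where T is persistence and C is available follow-up. That can never exceed T, so the summary is biased low wherever there is censoring.

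Follow-up varies widely here, so the bias differs by index date. Section 7 says that the use of DOACs, "particularly apixaban to treat VTE has increased dramatically". If apixaban patients are indexed later on average, their raw persistent days would be lower than those of warfarin patients even with identical stopping behaviour.

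The raw times to discontinuation and to switch have a related problem: they can be computed only in patients with an observed event, which favours early events.

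At stake is the headline number for a measure named in a main objective.

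**Working it through.** The plan states no expected persistence, event count or sample size calculation, so there is no figure to reproduce. The check concerns direction and plausible size.

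**Range of follow-up (from sections 9.1 and 9.1.1).** The selection window opens on 01 January 2018 and an overnight stay is required, so the earliest index date is 02 January 2018. With data to 31 December 2022, that gives 1,824 days. A discharge on 30 November 2022 with a first fill 30 days later gives an index date of 30 December 2022 and 1 day. A later data cut, which the protocol allows, would lengthen both.

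**Understatement within one cohort.** Assumptions: exponential time to stopping or switching, and index dates uniform over the window. The last column adds exponential loss of visibility with mean 365 days. Simulation, 400,000 patients per scenario:

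| True median (days) | Raw median, administrative censoring only | Raw median, with added loss |
|---|---|---|
| 90 | 84 | 63 |
| 180 | 157 | 97 |
| 365 | 279 | 133 |
| 730 | 440 | 162 |

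Kaplan-Meier on the composite returns about the true median in every row. With a true median of 180 days and administrative censoring only, the raw median is 180 for 2018 index dates and 98 for 2022; the Kaplan-Meier median is 180 in both years. When the true median is 365 days or more under administrative censoring alone, the Kaplan-Meier median for the 2022 index year is not reached.

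**Gap between cohorts with no true difference.** Assume T is exponential with mean m = 300 days in both cohorts. For C uniform on (a, b):

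E[min(T, C)] = m − m²(e^(−a/m) − e^(−b/m))/(b − a)

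- C uniform on 1 to 1,825 days: 300 − 90,000 × (0.9967 − 0.0023)/1,824 = 251.
- C uniform on 1 to 730 days: 300 − 90,000 × (0.9967 − 0.0877)/729 = 188.

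For linearly tilted index dates, E[min(T, C)] = m(1 − E[e^(−C/m)]). With L = 1,825:

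- Index dates rising linearly from zero, density of C = 2(L − c)/L²: about 218.
- Index dates falling linearly to zero, density of C = 2c/L²: about 284.

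| Index dates in the two cohorts | Raw means (days) | Gap (days) |
|---|---|---|
| Same distribution | equal | 0 |
| Uniform vs rising linearly | 251 vs 218 | about 33 |
| Uniform vs all in the last two years | 251 vs 188 | 63 |
| Falling vs rising linearly | 284 vs 218 | about 67 (66.5 unrounded) |

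The mean of T among patients with an observed event, E[T | T < C], is 242 days for C on 1 to 1,825 and 162 days for C on 1 to 730. The restricted mean to 180 days is 300 × (1 − e^(−0.6)) = 135 days whatever the index dates.

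**Do the separate curves supply the composite?** Only if the handling of the other event is known. Suppose the composite median is 208 days (300 × ln 2) and 20% of a constant hazard is switching. If switches are censored, the discontinuation curve has median 208/0.8 = 260 days, which overstates persistence.

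**The case against.** The strongest reply is that the plan already deals with censoring where it matters. Both events that end persistence have Kaplan-Meier medians with confidence intervals, and the general statement in section 9.6 gives them only as examples. The four planned regression models can be read as one for discontinuing or switching plus one for each of three clinical outcomes, which would make the composite a modelled endpoint. Discontinuation is defined by refills of the index drug alone, so a switcher who stops refilling may also count as discontinuing, and that curve could lie close to a persistence curve. The persistence bullet openly counts to the end of follow-up. No descriptive cohort comparison is planned, and index year and follow-up duration will be shown.

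Much of this stands. A reader might infer that persistence has no censoring-aware analysis at all; the documents do not support that. A reader might also infer that apixaban will look less persistent by some 63 days. That size requires every patient in one cohort to be indexed in the last two years while the other is spread evenly. The protocol says that apixaban use has risen but gives no index-date distribution by cohort.

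What remains is narrower. The count of models is a plausible reading that the text does not confirm, and a hazard ratio gives no duration in any case. How switchers enter the discontinuation curve is not stated. Showing follow-up duration discloses an imbalance without correcting the estimate, and the understatement arises within each cohort whether or not they are compared.

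**Conclusion.** The point holds in limited form. Followed as written, the plan's stated persistence figure is biased low, and lower for later index dates. No Kaplan-Meier duration is specified for the composite, and the two separate curves do not settle it. The direction follows from the definition wherever censoring occurs. The size rests on assumed exponential persistence and assumed index dates: small if persistence is short relative to follow-up (84 against 90 days), large if it is long or visibility is lost early (162 against 730 days).

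A spurious difference between cohorts is possible but not established, and it is zero if their index dates are alike. This should be corrected before analysis, but it does not undermine the treatment-pattern analyses as a whole.

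**What to change.** In sections 9.2.2 and 9.6:

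1. Add, by cohort, a Kaplan-Meier estimate of time to the first of discontinuation or switch: median with 95% CI, percentage persistent at prespecified times and, optionally, a restricted mean to a horizon supported in both cohorts. The fixed-time percentages matter because a median may not be reached.
2. Keep the raw persistent-days summary if wanted, labelled as observed time on therapy. Label the raw times to discontinuation and to switch as being among patients with the event.
3. State how switching is handled in the discontinuation curve (counted, censored or competing), and the reverse.
4. Note as a limitation that ending follow-up at the last prescription or last medical claim may be informative censoring. Kaplan-Meier removes the bias from unequal administrative follow-up, but not this.

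The cost is wording and slightly more output: standard SAS procedures on data already held. If the sponsor regards this as a major change to a primary endpoint analysis, section 9.6 calls for an amendment.
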